Only the patients who meet the eligibility criteria will proceed to implantation. All patients who do not meet the eligibility requirements will be promptly study exited. Study exit of these patients must be documented on the Study Exit form. The period of follow-up will be 6 months to assess the safety and performance before initiating the pivotal randomized clinical trial. All patients will continue to be followed annually during long term follow-up to a minimum of five years.

The study will be conducted in accordance with Code of Federal Regulations (CFR) Parts 11, 50, 54, 56 and 812. A progress report of the clinical outcomes will be prepared by the Data and Safety Monitoring Board (DSMB) following enrollment of the first five (5) patients and at least twice per year thereafter. The recommendation(s) from the DSMB may be circulated to each of the Investigation Review Boards (IRB) participating in the study upon request.

BACKGROUND

Heart Failure (HF) represents a major and growing public health concern in terms of incidence, prevalence, morbidity, mortality and economic cost. Chronic HF is predominantly the result of ischemic heart disease or idiopathic dilated cardiomyopathy.

Chronic HF is conventionally treated with drugs. However there are many circumstances where drug therapy is insufficient or where the heart has become refractory to drug therapy. Cardiac Resynchronization Therapy (CRT) is indicated in patients with HF who have ventricular dyssynchrony, commonly evidenced by a widened QRS complex. Resynchronization therapy is suitable for approximately 30% of moderate HF [(New York Heart Association (NYHA) Class III] patients, and has been shown to provide significant clinical improvement [as measured by NYHA Class, quality of life (QOL) score, 6 minute walk test, freedom from advanced heart failure treatments, etc.]¹. However, as many as 30% of patients who have CRT implants do not have a satisfactory response (“non-responders”). Further, many patients initially have a good response but then develop more advanced symptoms.

Heart transplantation is an effective therapy for end stage NYHA Class IV patients. However, the number of donor hearts falls short of meeting the needs of patients and many patients are excluded because of age (the upper limit for transplant being approximately 65 years)².

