The C-Pulse® System is indicated for use in patients with moderate to severe heart failure [American College of Cardiology/American Heart Association (ACC/AHA) Stage C; NYHA Class III/IV], who are refractory to optimal medical therapy. The C-Pulse® System is intended to relieve the symptoms of heart failure, improve quality of life and cardiac function. The C-Pulse® System is also indicated for use in patients who are non responders to CRT pacemaker therapy. It is intended for use in hospital and at home. It is not intended as a replacement for heart function; it is not life sustaining or life–supporting therapy. It does not preclude the use of other heart failure therapies, such as valve surgery, heart transplantation or LVAD.

SUMMARY OF IMPLANT PROCEDURE

The C-Pulse® Cuff and Sense Lead are implanted through a chest incision and without the use of cardiopulmonary bypass. Only a small pericardiotomy is required, limiting the

potential for bleeding and for post-operative adhesions. The ascending aorta is isolated and its circumference measured. The circumferential length is marked on the Cuff and the Cuff is wrapped around the aorta such that the inflating aspect of the Cuff is positioned on the outside curvature. The Cuff is then checked to fit the aorta conformably and that the circumferential marks are appropriate prior to securing of the wrap with sutures.

Interrupted ‘mattress’ sutures are recommended, placed with the Cuff ‘open’ and using the circumferential marks as guidance, and such that the inflation chamber of the Cuff is always visualized. A bipolar ECG Sense Lead is placed on the heart and the gas line of the Cuff and ECG Sense Lead are attached to the intra-corporeal “Y– connector” end of the Percutaneous Lead. The Percutaneous Lead is then tunneled out over the abdomen, the extra-corporeal end of the Lead having a Patient Connector permanently attached. Alternatively, the Percutaneous Lead may be tunneled retrograde and secondarily attached to the gas line and sense lead. The Percutaneous Lead is designed to be exchanged or removed if required, the latter eliminating the exit site. If removal occurs, the Cuff and Sense Lead will remain within the thorax with the gas line of the Cuff and the connector of the Sense Lead capped off and accessible with minimal surgery in the subcutaneous tissue of the abdominal area.

STUDY DESCRIPTION

DESIGN

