1. Allow refinement of clinical and physiological criteria for patient selection and refinement of protocols for the operative procedure and concomitant medical therapy and rehabilitation post-operatively – the results of the Feasibility Study will allow effective planning of a larger study to examine device efficacy
2. Develop predictors for adverse events and measures for minimizing the frequency and/or severity of such events
3. Determine the parameters of implantation, patient recovery, hospitalization, rehabilitation and home discharge
4. Determine the means to design a successful pivotal trial in regards to the anticipated randomization, feasibility of blinding, core lab procedures and data collection

PATIENT SELECTION

Inclusion Criteria

Patients of both genders who satisfy all inclusion and exclusion criteria are eligible for this clinical study. Patients must meet the following criteria:

1. Patient has ACC/AHA Stage C heart failure and remains in NYHA Class III - ambulatory Class IV despite optimal **medical** therapy. Patients must have stable, evidence-based optimal medical therapy for heart failure as defined below:
 - ACE inhibitor or ARB (Angiotensin Receptor Blocks) at least 30 days preceding implant or nitrate/hydralazine at the investigators discretion
 - Beta-blocker for at least 90 days and stable for 30 days preceding implant
Note: Stable is defined as no more than a 50% reduction or 100% increase in the medications listed above. Transition within a therapeutic class is allowed if the dose is equivalent.
2. Patient has left ventricular ejection fraction (LVEF) $\leq 35\%$
3. Patient has had Cardiac Resynchronization Therapy (CRT) for at least 90 days prior to enrollment or is not indicated for a CRT device
4. Patient has had an implanted cardio-defibrillator (ICD) at least 30 days prior to enrollment or is not indicated for ICD implantation.
5. Patient is at least 18 years of age and not older than 75 years
6. Patient six minute hall walk assessment between 100–350 meters
7. Patient understands the nature of the procedure, is willing to comply with associated follow-up evaluations, and provide written informed consent prior to the procedure

Exclusion Criteria

Candidates must be excluded from the study if any of the following are met:

1. Patient has any evidence of:
 - Ascending aortic calcification on posterior–anterior or lateral chest x-ray at initial screening
OR

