Prescribed drugs are to be maintained until the time of surgery unless instructed otherwise by the anesthetist. Prophylactic anti-coagulation should be stopped. Premed given per institutional protocol.

Cardiac Resynchronization Therapy (CRT)

Per the eligibility criteria a patient should not be enrolled earlier than 90 days following CRT implant. Patients enrolled with a CRT device must have the Cardiac Resynchronization Therapy continued during the follow up period. ICD Therapy should remain activated except during the surgical implantation.

Planning for Device and Percutaneous Tube Positioning

Have the patient try on the Vest and bag to determine the best exit site. The goal is to minimize trauma to the exit site and to maximize patient comfort. Pay particular attention to the costal margins, belt line, and impact of sitting and standing and lying, and the exit site when wearing the Driver. The distance of the exit site from the costal margin should be considered in relation to the thickness of subcutaneous tissue, in order to prevent the percutaneous tube from rubbing against the costal margin. Also consider patients who inject insulin into the abdominal area. Mark the exit site.

Antisepsis Prophylaxis

Administer prophylactic antisepsis coverage. Recommended prophylaxis:

- Vancomycin 15mg/kg IV one hour pre-op given over 30 minutes and with minimum 5 minute interval blood pressure monitoring or arterial line monitoring – note that Vancomycin can cause hypotension in this patient population and should not be given unsupervised pre-operatively on the ward. Follow-up doses Q12–24 hr post-operatively for 48 hrs, guided by serum Vancomycin trough levels.
- Keflex 1g IV one hour pre-op then Q8–12hr for 48 hrs
- Rifampicin 600 mg PO 2hrs pre-op then daily for 2 days – stop if liver function tests become deranged greater than two times baseline
- Nasal Bactroban application day prior to surgery

Note: Record all drugs and doses on the Medication eCRF.

Prepare and shave the patient: Pre-operative scrub with antiseptic (Septisol or Chlorhexidine) on the night prior to surgery then again the morning of the surgery, and clip and shave the surgical area prior to transport to the operating room.

Observe Operating Room precautions – particularly, limit the number of people in the room, and traffic in and out of the room.

Baseline Procedures

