Infection localized to any organ system or region (e.g.) without evidence of systemic involvement (see sepsis definition), ascertained by standard clinical methods and either associated with evidence of bacterial, viral, fungal or protozoal infection, and/or requiring empirical treatment.

Percutaneous Site and/or Pocket Infection

A positive culture from the skin and/or tissue surrounding the drive line or from the tissue surrounding the external housing of a pump implanted within the body, coupled with the need to treat with antimicrobial therapy, when there is clinical evidence of infection such as pain, fever, drainage, or leukocytosis.

Internal Pump Component, Inflow or Outflow Tract Infection

Infection of the implanted C-Pulse Cuff documented by positive site culture.

Sepsis

Evidence of systemic involvement by infection, manifested by positive blood cultures and/or hypotension.

Myocardial Infarction

Two categories of myocardial infarction will be identified:

Peri-Operative Myocardial Infarction

The clinical suspicion of myocardial infarction together with CK-MB or Troponin > 10 times the local hospital upper limits of normal, found within 7 days following implant together with ECG findings consistent with acute myocardial infarction.

Non-Perioperative Myocardial Infarction

The presence at > 7 days post-implant of two of the following three criteria:

- a) Chest pain which is characteristic of myocardial ischemia,
- b) ECG with a pattern or changes consistent with a myocardial infarction, and
- c) Troponin or CK (measured by standard clinical pathology/laboratory medicine methods) greater than the normal range for the local hospital with positive MB fraction ($\geq 3\%$ total CK). This should be accompanied by a new regional LV or RV wall motion abnormality on a myocardial imaging study.

Neurological Dysfunction

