- Freedom to disconnect from the external driver for short periods of time before noticing return of symptoms, particularly shortness of breath
- Anti-coagulants not required
- Increased diastolic coronary artery blood flow
- Reduced systolic pulmonary artery pressures and mitral regurgitation
- Increased cardiac index
- Straightforward implant surgery
- No cardio-pulmonary bypass
- Avoid risk of lung and right heart complications associated with cardiopulmonary bypass – critical in patients with HF
- Preserved pericardial sac around ventricles
- Modular design
- Implanted device is very small
- There is no ‘pocket’ created
- Device can be removed and infection treated if necessary
- Subcutaneous line is long, and multiple flocking anchors are provided
- Line exiting skin is made of biostable and biocompatible materials, is soft and flexible, and can be removed and/or replaced

Overall advancement of medical and scientific knowledge that may benefit future patients may also be realized from this study.

There may also be other benefits that are unforeseen at this time.

Justification for the Investigation

The ethical conduct of a clinical trial of a new therapy relies on the promise the therapy has some benefit, but its efficacy to achieve this benefit is unknown and the new therapy always carries some risk (clinical equipoise).³⁵ A careful and complete presentation of the scientific merit for the trial, including evidence both for and against the investigational treatment, forms the ethical basis for the study design and conduct.

Clinical Need

There are over 1.4M people in the USA in Class III and IV heart failure. Biventricular pacemakers are indicated in patients with a wide QRS – approximately 30% of this population. Approximately 2200 heart transplants are done per year. A similar number might receive an LVAD as either a bridge to transplant or as destination therapy.

There remain a very large number of people that may benefit from an improvement in their clinical status from NYHA Class III/IV to Class I/II. The targeted Patient population is defined by the expected natural history of heart failure. [Figure 2](#) highlights the trend of heart failure, and the relationship of severity of heart failure with repeat hospitalization and with mortality.

[figure not shown]

Figure 2. Annual survival rate and frequency of hospitalizations versus NYHA Classification

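### The peri-operative MI definition requires ECG findings and has no rule for an uninterpretable ECG, so the stand-alone MI rate can read low in patients on continued CRT

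*Combined protocol and SAP*

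**What the plan says.** Under Adverse Event Definitions, Peri-Operative Myocardial Infarction has three joined elements: clinical suspicion, CK-MB or troponin more than 10 times the local upper limit, and an ECG element, "found within 7 days following implant together with ECG findings consistent with acute myocardial infarction". All three are needed.

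The companion definition for later infarction is looser: "The presence at > 7 days post-implant of two of the following three criteria". Chest pain and the biomarker criterion can satisfy it without the ECG. Its biomarker criterion also asks for a new wall motion abnormality on imaging.

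On CRT, Inclusion Criteria item 3 reads: "Patient has had Cardiac Resynchronization Therapy (CRT) for at least 90 days prior to enrollment or is not indicated for a CRT device". Pre-Implant Considerations adds: "Patients enrolled with a CRT device must have the Cardiac Resynchronization Therapy continued during the follow up period". Indications for Use names a target group: "The C-Pulse® System is also indicated for use in patients who are non responders to CRT pacemaker therapy".

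MI is a component of the six-month composite under Primary Safety Measures. That composite counts only events the CEC judges device-related, and it ends with a residual category for other device-related events. Performance Requirements and Secondary Objectives also give each event its own rate and exact 95% interval. The Data and Safety Monitoring Board (DSMB) judges acceptability clinically, with no numerical threshold.

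**The concern.** Ventricular pacing changes the QRS and ST-T pattern, so an acute infarct pattern may not be readable. That is general ECG knowledge and is not stated in the plan. If it happens, a patient with clinical suspicion and a biomarker above the threshold fails the third element and is recorded as having no peri-operative MI. The definition offers no substitute evidence and no code for a case that cannot be assessed.

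What is at stake is the MI row and its interval. The gap covers the first 7 days after implant, the period of the surgery itself. The DSMB sees small counts without a threshold, so moving from no event to one event matters to how the table is read. Under this mechanism true infarctions are only removed, so the error runs downward.

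**Working it through.** There is no planned figure to reproduce. The sample size is a clinical judgement without a formula, and no expected MI rate is given. The check is therefore a range under stated assumptions.

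**Inputs**
- n = 40 implants (Study Size and Duration, expansion). Sample Size Determination still refers to 20; expected counts at 20 are half those below.
- c = share of trial patients on CRT. Not stated.
- s = share of true infarctions in CRT patients whose ECG still meets the criterion. Not stated; 0.5 and 0 are used.
- p = true peri-operative MI rate. Not stated; 5% and 10% are used.

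**Two readings of c from the plan's background figures**
- Background: "Resynchronization therapy is suitable for approximately 30% of moderate HF". Clinical Need: "Biventricular pacemakers are indicated in patients with a wide QRS – approximately 30% of this population". If enrolment mirrors that share and every indicated patient has CRT, c = 30%, or 12 of 40.
- Background also says "as many as 30% of patients who have CRT implants do not have a satisfactory response". If only those non-responders stay symptomatic enough to enrol, c = (0.3 × 0.3) / (0.3 × 0.3 + 0.7) = 0.09 / 0.79 = 11.4%, or about 4.6 of 40.

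Neither is a bound. Later worsening in initial responders, which Background mentions, and the targeting of non-responders push c up. The non-response figure is itself a maximum, which pulls the second reading down.

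**Formulas**
- Recorded rate = p × [1 − c(1 − s)]
- Expected missed = n × p × c × (1 − s)
- Chance of missing at least one = 1 − [1 − p × c × (1 − s)]^n

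**Results, n = 40**

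| c | s | p | Recorded rate | Expected missed | Chance of missing at least one |
|---|---|---|---|---|---|
| 11.4% | 0.5 | 5% | 4.7% | 0.11 | 11% |
| 11.4% | 0 | 5% | 4.4% | 0.23 | 20% |
| 11.4% | 0 | 10% | 8.9% | 0.46 | 37% |
| 30% | 0.5 | 5% | 4.25% | 0.30 | 26% |
| 30% | 0.5 | 10% | 8.5% | 0.60 | 45% |
| 30% | 0 | 5% | 3.5% | 0.60 | 45% |
| 30% | 0 | 10% | 7.0% | 1.20 | 70% |

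If every paced ECG is readable (s = 1), nothing is missed.

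**Scale against sampling error**
- Smallest case: bias 0.05 × 0.114 × 0.5 = 0.00285; standard error √(0.05 × 0.95 / 40) = 0.0345; ratio 0.08.
- Largest case: bias 0.10 × 0.30 = 0.03; standard error √(0.10 × 0.90 / 40) = 0.0474; ratio 0.63.
- Exact 95% intervals: 0/40 gives 0 to 8.8%, and 1/40 gives 0.1 to 13.2%. One missed event moves the upper limit by 4.4 percentage points, well inside the interval's width.

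**The case against.** The strongest objection is that the event need not disappear. A device-related infarction that fails the MI definition can still enter the composite through the residual category. An infarction that results directly from the surgery, and is not attributable to the device, is procedure-related under Adverse Event Classification and lies outside the composite whatever the ECG shows. The catch-all category Other can also hold it. This stands: a reader might infer that the primary composite is biased, and the documents do not support that. What remains is misplacement between rows, which lowers the MI row.

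A reader might also infer that, by the plan's own figure, about 30% of trial patients are paced. The 30% describes the wider heart failure population for whom CRT is suitable or indicated. Item 3 makes it a possible inference for the trial, but it is not a stated trial figure.

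The definition follows the Intermacs registry, Version 2.2, and comparability has value. That stands as a reason to keep the registry row, not as a reason against a second one. The protocol already departs from the registry for Major Bleeding and adds Aortic Disruption.

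Finally, the section on the CEC calls for a charter with a classification algorithm. It is not among the documents and may cover this case. The protocol definition does not.

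**Conclusion.** The gap is real and limited. Followed exactly, the peri-operative definition can exclude a suspected, biomarker-positive infarction because the ECG cannot be interpreted, and the CRT requirements make such ECGs foreseeable. The event-specific MI rate and its exact interval can therefore read low; the primary composite need not.

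The size cannot be fixed from the documents. With 40 implants, the expected number of missed infarctions runs from about 0.1 (11% on CRT, half of ECGs readable, true rate 5%) to 1.2 (30% on CRT, none readable, true rate 10%). The upper end is a worst case. All three inputs are assumptions, and the mechanism rests on general ECG knowledge. Even at the upper end the bias is about 0.6 of a standard error, so it affects how one safety row is read and does not invalidate the study.

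**What to change.** Have the CEC code each suspected peri-operative MI as ECG interpretable or not interpretable. Keep the MI row under the registry definition. Beside it, report a second row with its own exact interval. This row also counts cases with clinical suspicion, a biomarker above 10 times the upper limit and an uninterpretable ECG, and notes whether any clinically obtained imaging showed a new regional wall motion abnormality. Show MI by CRT status, so that the number of patients exposed to the problem is visible.

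Imaging should be noted and not required. Table 3 schedules no transthoracic echocardiogram between baseline and 1 month, the implant study is epi-aortic, and the Echocardiographic Testing list does not name regional wall motion. A rule that simply replaced the ECG with wall motion evidence would still miss patients who happened not to be imaged.

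The cost is one CEC code, one extra table row and one split by CRT status, with no new test. The downside is that the second row is not the registry definition and may count some biomarker rises that are not infarctions, which is why both rows are shown.
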